6.5 Dose modifications

For participants who do not tolerate the protocol-specified dosing schedule, dose interruptions are permitted in order to allow participants to continue the study treatment. All dose modifications, interruptions or discontinuations must be based on the worst preceding toxicity as graded by the NCI Clinical Toxicity Criteria (NCI-CTCAE version 5.0). Any changes must be recorded on the dose administration eCRF page.

Dose reductions are allowed for capmatinib and should follow the dose reduction steps described in [Table 6-2](#) and [Table 6-3](#). For each participant, a maximum of two consecutive dose level reductions is allowed after which the participant must be discontinued. Dose reductions of capmatinib below 200 mg b.i.d are not permitted. The lowest dose allowed, 200 mg b.i.d. in tablets is expected to be pharmacologically active, as the observed steady state plasma trough concentrations ([CINC280X1101], [CINC280X2202], n=6) were above the concentration associated with full MET inhibition in xenograft mice models (IC90, 120 nM total concentration).

A participant must discontinue treatment with capmatinib if, after treatment is resumed at the lowest allowed dose (200 mg b.i.d.), the toxicity recurs with the same or worse severity despite use of maximal preventive measures as per the institution guidelines for toxicity prevention and management.

Unless otherwise indicated in [Table 6-3](#), for grade 1 and tolerable grade 2 treatment-related toxicities, participants may continue full doses of capmatinib. For intolerable grade 2 or grade 3 treatment-related toxicities, dosing should be interrupted until at least resolution to grade 1

followed by either dose reduction or re-initiation at the same dose level, depending on the type of toxicity as described in [Table 6-3](#). For any grade 4 toxicity, except for neutropenia, febrile neutropenia, anemia and thrombocytopenia, participants should interrupt capmatinib until resolution to grade 1, followed by either dose reduction or treatment discontinuation (refer to [Table 6-3](#)).

Permanent treatment discontinuation is mandatory for specific events indicated in [Table 6-3](#). Deviations to mandatory dose discontinuations are not allowed.

All interruptions or changes to study drug administration must be recorded in the dose administration eCRF.

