Dose re/escalation of study treatment to previous dose level is allowed only once, and if no AE leading to dose modification is observed after at least 1 cycle (4 weeks) of study treatment at the reduced dose.

Any planned variance from the guidelines in [Table 6-3](#), in view of participant safety (unless there is an urgent need for action) when in the opinion of the investigator the participant continues to experience clinical benefit, should first be discussed and approved by the Novartis Medical Lead or designee.

Events not included in the study protocol or the reference guidance documents should be managed according to local practices. All dose changes must be recorded on the appropriate eCRF.

Table 6-2 Dose reduction steps for capmatinib

	Starting dose level 0	Dose level -1	Dose level -2
capmatinib	400 mg b.i.d	300 mg b.i.d	200 mg b.i.d

Note: dose reduction should be based on the worst toxicity demonstrated at the last dose. Dose reduction below 200 mg is not allowed.

Table 6-3 Criteria for dose reduction / interruption and re-initiation/ permanent discontinuation of capmatinib treatment for adverse drug reactions

Dose modifications for capmatinib	
Worst toxicity CTCAE Grade^a	During a cycle of therapy
No toxicity	Maintain dose level
HEMATOLOGICAL	
Neutrophil count decreased (ANC) Neutropenia	
Grade 1 (ANC < LLN - 1500/mm ³ ; < LLN - 1.5 x 10 ⁹ /L)	Maintain dose level
Grade 2 (ANC < 1500 - 1000/mm ³ ; < 1.5 - 1.0 x 10 ⁹ /L)	Maintain dose level
Grade 3 (ANC < 1000 - 500/mm ³ ; < 1.0 - 0.5 x 10 ⁹ /L)	Omit dose until resolved to ≤ grade 2, then: 
 • If resolved in ≤ 7 days, resume treatment at the same dose level • If resolved in > 7 days, then ↓ 1 dose level

Grade 4 (ANC < 500/mm ³ ; < 0.5 x 10 ⁹ /L)	Omit dose until resolved to ≤ grade 2 and then ↓ 1 dose level
Platelet count decreased (Thrombocytopenia)	
Grade 1 (PLT < LLN - 75,000/mm ³ ; < LLN - 75 x 10 ⁹ /L)	Maintain dose level
Grade 2 (PLT < 75,000 - 50,000/mm ³ ; < 75 - 50 x 10 ⁹ /L)	Maintain dose level
Grade 3 (PLT < 50,000 - 25,000/mm ³ ; < 50 - 25 x 10 ⁹ /L)	Omit dose until resolved to ≤ grade 2, then: 
 • If resolved in ≤ 7 days, then maintain dose level • If resolved in > 7 days, then ↓ 1 dose level
Grade 4 (PLT < 25,000/mm ³ ; < 25 x 10 ⁹ /L)	Omit dose until resolved to ≤ grade 2, then ↓ 1 dose level

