Combined elevations of AST or ALT and Total bilirubin^{b,d}	
For participants with normal baseline ALT and AST and TBL value: AST or ALT > 3.0 x ULN combined with TBL > 2.0 x ULN without evidence of cholestasis ^c Or hemolysis OR For participants with elevated baseline AST or ALT or TBL value: [AST or ALT > 3 x baseline] OR [AST or ALT > 8.0 x ULN], whichever is lower, combined with [TBL > 2 x baseline AND > 2.0 x ULN]	Mandatory: Permanently discontinue participant from study drug treatment
METABOLIC	
Amylase and/or lipase elevation	
Grade 1 (> ULN - 1.5 x ULN)	Maintain dose level
Grade 2 (> 1.5 - 2.0 x ULN; > 2.0 - 5.0 x ULN and asymptomatic)	Maintain dose level
Grade 3 (> 2.0 - 5.0 x ULN with signs or symptoms; > 5.0 x ULN and asymptomatic)	Omit the dose until resolved to \leq grade 2, then 
 • If resolved in \leq 14 days, resume treatment at the same dose level • If resolved in > 14 days, then \downarrow 1 dose level
Grade 4 (> 5.0 x ULN and with signs or symptoms)	Permanently discontinue participant from study drug treatment
CARDIAC	
Electrocardiogram QT corrected (QTc) interval prolonged	
Grade 1 (QTcF 450-480 ms) and	Maintain dose level

Grade 2 (QTcF 481-500 ms)	
Grade 3 (QTcF \geq 501 ms on at least two separate ECGs)	Omit dose until resolved to \leq grade 2, then: 
 • If resolved in \leq 7 days, resume treatment at the same dose level • If resolved in $>$ 7 days, then \downarrow 1 dose level
Grade 4 (QTcF \geq 501 or $>$ 60 ms change from baseline and Torsades de pointes or polymorphic ventricular tachycardia or signs/symptoms of serious arrhythmia)	Permanently discontinue participant from study drug treatment
GASTROINTESTINAL	
Pancreatitis	
Grade 2	Maintain dose level
Grade \geq 3	Permanently discontinue participant from study drug treatment
Diarrhea**	
Grade 1 (despite maximal anti-diarrheal medication)	Maintain dose level
Grade 2 (despite maximal anti-diarrheal medication)	Omit dose until resolved to \leq grade 1, then maintain dose level. 
 • If diarrhea returns as \geq grade 2, then omit dose until resolved to \leq grade 1, then resume treatment at \downarrow 1 dose level
Grade 3 or 4 (despite maximal anti-diarrheal medication)	Omit dose until resolved to \leq grade 1, then resume treatment at \downarrow 1 dose level
Vomiting	
Grade 1 (despite appropriate anti-emetics)	Maintain dose level

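### For five grade 3 toxicities, the text of Section 6.5 and Table 6-3 give different recovery grades for restarting capmatinib, and the protocol does not say which governs

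*Protocol*

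**What the plan says.** The text of protocol Section 6.5 sets general rules by grade.

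- Grade 1 and tolerable grade 2: "for grade 1 and tolerable grade 2 treatment-related toxicities, participants may continue full doses of capmatinib". This sentence opens with a proviso that yields to Table 6-3.
- Intolerable grade 2 and grade 3: "For intolerable grade 2 or grade 3 treatment-related toxicities, dosing should be interrupted until at least resolution to grade 1". The rest of that sentence leaves the restart dose, reduced or unchanged, to Table 6-3 according to the toxicity.
- Grade 4: "For any grade 4 toxicity, except for neutropenia, febrile neutropenia, anemia and thrombocytopenia, participants should interrupt capmatinib until resolution to grade 1". After that the dose is reduced or treatment stops, with a reference to Table 6-3.

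Table 6-3 then gives rules by toxicity. For grade 3 neutropenia, thrombocytopenia and anemia the row reads: "Omit dose until resolved to ≤ grade 2, then", with the restart dose depending on whether resolution took more than 7 days. The grade 3 rows for amylase/lipase and for QTc prolongation use the same recovery grade, with a 14-day and a 7-day cut respectively.

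Three other places bear on the point. Section 6.5.1 says that Tables 6-3 and 6-2 are to be followed when capmatinib is withheld for toxicity. It also says that a hold of more than 21 consecutive days should end treatment, unless the sponsor approves an exception. Section 6.5 requires sponsor approval for planned variance from Table 6-3. Table 6-4 sets the extra testing after selected toxicities.

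**The concern.** The recovery grade decides when a participant may restart. If two parts of one section give different grades for the same event, two sites can both follow the protocol and hold drug for different lengths of time. The longer hold uses up more of the 21 days in Section 6.5.1, so the choice of text can also bear on whether treatment continues.

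The blood-count exemption adds to the difficulty. It is written into the grade 4 sentence and is absent from the grade 3 sentence. Someone reading only the text would conclude that grade 3 neutropenia has to reach grade 1, while grade 4 neutropenia is sent to the table, where grade 2 is enough.

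**Working it through.** The plan states no figure on this point, so the check is a row-by-row comparison.

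**1. Classify every grade 3 entry of Table 6-3.** Febrile neutropenia is ungraded and is left out.

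- Restart at grade 2 or below: neutropenia, thrombocytopenia, anemia, amylase/lipase, QTc = 5.
- Restart at grade 1 or below: creatinine (or baseline), bilirubin, AST/ALT, diarrhea, vomiting, nausea, rash/photosensitivity, fatigue, peripheral edema, other AEs = 10.
- Permanent discontinuation: pancreatitis, ILD/pneumonitis = 2.
- Total: 5 + 10 + 2 = 17.

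AST/ALT is a conditional sixth case, because its row accepts grade 2 if the baseline was grade 2. Entry caps AST and ALT at 3 x ULN at screening, and grade 2 starts above 3 x ULN, so this should seldom arise.

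**2. Put the two conditions side by side**, using the grade limits printed in Table 6-3.

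| Grade 3 event | Text of 6.5 (grade 1) | Table 6-3 (grade 2 or below) |
|---|---|---|
| Neutrophils, x 10^9/L | at least 1.5 | at least 1.0 |
| Platelets, x 10^9/L | at least 75 | at least 50 |
| Hemoglobin, g/dL | at least 10.0 | at least 8.0 |
| Amylase/lipase, x ULN | at most 1.5 | at most 2.0, or 5.0 if asymptomatic |
| QTcF, ms | at most 480 | at most 500 |

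**3. Check the grade 4 sentence.** Outside blood counts, the table's grade 4 rows either discontinue or, for diarrhea and vomiting, restart at grade 1 or below. The grade 4 blood-count rows restart at grade 2 or below, one dose level lower, and the text exempts them. The grade 4 sentence therefore agrees with the table on recovery grade. The grade 3 sentence does not.

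**4. Compare grade 3 with grade 4 for blood counts.** Under the table alone, both have the same recovery grade. With the text at grade 3 and the table at grade 4, grade 3 must reach 1.5, 75 and 10.0, while grade 4 need reach only 1.0, 50 and 8.0.

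**5. Compare with entry criteria.** Entry allows hemoglobin from 9 g/dL and asymptomatic amylase up to grade 2. The grade 3 sentence has no baseline exception. A participant who enters at 9.5 g/dL and falls to 7.8 would have to reach 10.0, which is above baseline.

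**6. Work out what the difference does to a hold.** Let t2 and t1 be the days from the start of the hold to grade 2 and to grade 1, with t1 no smaller than t2. The extra hold under the text is t1 - t2. The two rules differ on the 21-day limit only when t2 is at most 21 and t1 is more than 21. The documents give no recovery times, so the frequency cannot be stated. As an assumed illustration, neutrophils of 0.8 reach grade 2 on day 5 and grade 1 on day 10. The extra hold is 10 - 5 = 5 days, or 5/56 = 8.9% of the 8-week neoadjuvant course.

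**7. Compare with Table 6-4.** Weekly (or more frequent) testing for grade 3 or higher blood counts, asymptomatic amylase/lipase and cardiac events is required only until grade 2 or below. Under the text, the mandated extra testing stops before the restart condition is met. Scheduled visits from Cycle 4 are three months apart.

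**The case against.** The best defence is that the protocol already leans on the table. Section 6.5.1 directs sites to Tables 6-3 and 6-2 for exactly this case, a hold for toxicity. Planned variance from Table 6-3 needs approval, Table 6-4 stops extra testing at the same grade as Table 6-3, and the table's title covers re-initiation. On that view the grade 3 sentence is a loose summary. This has weight, and many sites would probably go to the table. But none of these places withdraws the sentence or ranks it below the table.

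A second defence is that the proviso yielding to Table 6-3 was meant for the whole paragraph. As written, it belongs to the sentence on grade 1 and tolerable grade 2. If it covered everything, the separate blood-count exception at grade 4 would be unnecessary.

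Some stronger readings are tempting and should not be drawn:

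- **The milder event takes longer in days.** A grade 4 event starts from a worse value, so the documents show only a lower recovery grade. Even that requires the text at grade 3 and the table at grade 4.
- **In the illustration above, the text would also take the participant from 400 to 300 mg b.i.d.** The 7-day cut in the neutropenia row belongs to resolution to grade 2 or below, which is met on day 5. The text leaves the restart dose to the table. The drop appears only if the text's grade 1 is put into the table's clock, which neither place says.
- **A milder grade should never have the stricter condition.** That is a clinical rule for the sponsor, and the documents do not state it.

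On scale, the protocol summary calls myelosuppression uncommon with capmatinib, and three of the five rows are blood counts.

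**Conclusion.** Wrong as written, and minor. The text of Section 6.5 and Table 6-3 give different recovery grades for five of 17 grade 3 entries, with AST/ALT a conditional sixth. The protocol does not say which one governs. What follows is a longer hold for anyone treated under the literal text, with the extra days counted towards the 21-day limit.

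This rests on reading the proviso as attached only to its own sentence. It also applies only to treatment-related toxicity, to which the grade 3 sentence is confined.

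The reach is small. The SAP reports that recruitment stopped with four participants and that dosing data will be listed without summary. A reader might infer a distorted tolerability analysis, since protocol Section 12.5.2 planned to summarise interruptions and reductions, but under the SAP no such summary remains. Individual hold durations in the listings could still reflect whichever rule a site followed. No view is taken here on which recovery grade is right.

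**What to change.** Reconcile the grade 3 and grade 4 sentences of Section 6.5 with the Table 6-3 rows, and check the result against Section 6.5.1 and the testing endpoints in Table 6-4. Each toxicity should end with one recovery condition. Add a sentence stating which governs wherever the general text and the table differ, and place any proviso so that its scope is clear. The sponsor's clinical team must choose the thresholds.

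The cost is the wording of one paragraph or of the affected rows. Section 14.1 requires a written amendment for any protocol change, so this could travel with the next one. If nobody remains on treatment, a note in the study report on which restart rule sites applied would be enough for reading the dosing listings.

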5.1 Inclusion criteria

Participants eligible for inclusion in this study must meet **all** of the following criteria:

1. Signed informed consent must be obtained prior to participation in the study.
2. Adult ≥ 18 years of age at the time of informed consent.
3. Histologically confirmed NSCLC stage IB-IIIA, N2 and selected IIIB (T3N2 or T4N2) (per AJCC 8th edition), deemed suitable for primary resection by treating surgeon (T4 tumors with mediastinal organ invasion are not eligible for enrollment).
4. Participant must have MET exon 14 mutation and/or high level MET amplification (MET: GCN ≥ 10) as determined by a CLIA certified laboratory. High level MET amplification must be identified by FISH in a CLIA certified laboratory or FoundationOne CDx NGS (other NGS-based methods without adjusting for tumor content % cannot be accepted).
5. Participants must be eligible for surgery and scheduled for surgical resection within approximately 2 weeks after the last dose of neoadjuvant study treatment.
6. Participants must have adequate organ function including the following laboratory values at the screening visit:
 - Absolute neutrophil count (ANC) $\geq 1.5 \times 10^9/L$ without growth factor support
 - Platelets $\geq 100 \times 10^9/L$
 - Hemoglobin (Hgb) $\geq 9 \text{ g/dL}$
 - Calculated creatinine clearance (using Cockcroft-Gault formula) $\geq 45 \text{ mL/min}$
 - Total bilirubin (TBIL) $\leq 1.5 \text{ ULN}$ (upper limit of normal)
 - Aspartate transaminase (AST) $\leq 3 \times \text{ULN}$
 - Alanine transaminase (ALT) $\leq 3 \times \text{ULN}$
 - Asymptomatic serum amylase $\leq 5 \times \text{ULN}$ (Grade 2). Participants with Grade 1 or Grade 2 serum amylase at the beginning of the study must be confirmed to have no signs and/or symptoms suggesting pancreatitis or pancreatic injury (e.g. elevated P-amylase, abnormal imaging findings of pancreas, etc.)
 - Serum lipase $\leq \text{ULN}$

- Alkaline phosphatase (ALP) $\leq 5.0 \times$ ULN

7. Participant must have adequate cardiovascular and respiratory function to be submitted to surgical procedure as assessed per local clinical practice, including:

- Adequate pulmonary function to be eligible for surgical resection. Postoperative predicted forced expiratory volume in 1 second (FEV1) and diffusion capacity must be $\geq 40\%$ and/or maximal oxygen consumption (VO₂ max) should be > 10 mL/kg/min.

8. ECOG PS of 0 or 1.

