Febrile neutropenia (ANC < 1000/mm ³ (< 1.0 x 10 ⁹ /L), fever > 38.3°C)	Omit dose, then: 
 • If resolved in ≤ 7 days, resume treatment at ↓ 1 dose level • If resolved in > 7 days, permanently discontinue participant from study drug treatment
Hemoglobin decreased (Anemia)	
Grade 1 (Hgb < LLN - 10.0 g/dL; < LLN - 6.2 mmol/L; < LLN - 100 g/L)	Maintain dose level
Grade 2 (Hgb < 10.0 - 8.0 g/dL; < 6.2 – 4.9 mmol/L; < 100 - 80 g/L)	Maintain dose level
Grade 3 (Hgb < 8.0 g/dL; < 4.9 mmol/L; < 80 g/L)	Omit dose until resolved to ≤ grade 2, then: 
 • If resolved in ≤ 7 days, resume treatment at the same dose level • If resolved in > 7 days, then ↓ 1 dose level
Grade 4 (Life-threatening consequences; urgent intervention indicated)	Omit dose until resolved to ≤ grade 2 and then ↓ 1 dose level If toxicity recurs, permanently discontinue participant from study drug treatment.
RENAL	
Serum creatinine	
Grade 1 (> ULN - 1.5 x ULN)	Maintain dose level
Grade 2 (> 1.5 - 3.0 x ULN)	Omit dose until resolved to ≤ grade 1 or baseline, then resume treatment at the same dose level.
Grade 3 (> 3.0 - 6.0 x ULN)	Omit dose until resolved to ≤ grade 1 or baseline, then resume treatment at ↓ 1 dose level.
Grade 4 (> 6.0 x ULN)	Permanently discontinue participant from study drug treatment
HEPATIC	
Isolated Total bilirubin elevation*	
Grade 1 (> ULN - 1.5 x ULN)	Maintain dose level

Grade 2 (> 1.5 - 3.0 x ULN)	Omit dose until resolved to \leq grade 1, then: 
 • If resolved in \leq 7 days, maintain dose level • If resolved in > 7 days, \downarrow 1 dose level
Grade 3 (> 3.0 - 10.0 x ULN)	Omit dose until resolved to \leq grade 1, then: 
 • If resolved in \leq 7 days, \downarrow 1 dose level • If resolved in > 7 days, permanently discontinue capmatinib
Grade 4 (> 10.0 x ULN)	Permanently discontinue participant from study drug treatment
Isolated AST or ALT elevation	
Grade 1 (> ULN - 3 x ULN)	Maintain dose level
Grade 2 (> 3.0 - 5.0 x ULN)	Maintain dose level
Grade 3 (> 5.0 - 20.0 x ULN)	Omit dose until resolved to \leq grade 1 (or \leq grade 2 if grade 2 elevation at baseline) then: 
 • If resolved in \leq 7 days, then resume treatment at the same dose level • If resolved in > 7 days, resume treatment at \downarrow 1 dose level
Grade 4 (> 20.0 x ULN)	Mandatory: Permanently discontinue participant from capmatinib treatment

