All dose modifications should be based on the worst preceding toxicity. a Common Toxicity Criteria for Adverse Events (CTCAE Version 5.0). b "Combined" defined as: TBL increase to the defined threshold concurrently with ALT/AST increase to the defined threshold c "Cholestasis" defined as: ALP elevation ($> 2.0 \times$ ULN and R value (ALT/ALP in \times ULN) < 2.0) in participants without bone metastasis, or elevation of ALP liver fraction in participants with bone metastasis d If combined elevations of AST or ALT and TBL do not meet the defined thresholds, please follow the instructions for isolated elevation of TBL and isolated elevation of AST/ALT, and take a conservative action based on the degree of the elevations (e.g. discontinue treatment at the situation when omit dose is needed for one parameter and discontinue treatment is required for another parameter). After all elevations resolve to the defined thresholds that allow treatment re-initiation, re-start the treatment either at the same dose or at one dose lower if meeting a criterion for dose reduction * Note: If TBL $> 3.0 \times$ ULN is due to the indirect (non-conjugated) component only, and hemolysis as the etiology has been ruled out as per institutional guidelines (e.g., review of peripheral blood smear and haptoglobin determination), then \downarrow 1 dose level and continue treatment at the discretion of the investigator. ** Note: antidiarrheal medication is recommended at the first sign of abdominal cramping, loose stools or overt diarrhea *** During the whole duration of treatment with capmatinib, the participant is recommended to use precautionary measures against ultraviolet exposure (e.g., use of sunscreen, protective clothing and avoid sunbathing or using a solarium intensively).	

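### A raised ALP that predates treatment can count as cholestasis in Table 6-3 and so hold back the mandatory combined ALT/AST and bilirubin stop

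*Protocol*

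**What the plan says.** The rule is built from four places in the Protocol.

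- **Entry (5.1, criterion 6).** ALP is accepted up to 5.0 x ULN. Metastatic disease is excluded (5.2, criterion 1).
- **Combined row of Table 6-3.** The first limb is chosen by normal baseline ALT, AST and TBL; baseline ALP plays no part. It mandates permanent discontinuation for ALT or AST above 3 x ULN with "TBL > 2.0 x ULN without evidence of cholestasis" or hemolysis. The second limb, for a raised baseline ALT, AST or TBL, judges bilirubin as "TBL > 2 x baseline AND > 2.0 x ULN" and, as printed, carries no cholestasis exception.
- **Footnote c.** Cholestasis is ALP above 2.0 x ULN with R below 2.0 "in participants without bone metastasis, or elevation of ALP liver fraction in participants with bone metastasis". Section 6.5.2.1 repeats this and defines R as ALT divided by ALP, each as a multiple of ULN. It adds that GGT can be used when an extrahepatic source of ALP is suspected.
- **Footnote d.** "If combined elevations of AST or ALT and TBL do not meet the defined thresholds", the isolated TBL and ALT/AST rows apply, and the site is to "take a conservative action based on the degree of the elevations". The footnote also provides for restart once values have resolved.

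Section 6.5 allows no deviation from mandatory discontinuations, whereas other planned variances from Table 6-3 can be approved by the sponsor.

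**The concern.** The cholestasis exception separates a bile-flow problem from hepatocellular injury. A high ALP that was there before the drug and has not moved says nothing about the cause of a new ALT and bilirubin rise. Because footnote c looks only at the current multiple of ULN, it treats that old ALP as evidence of cholestasis.

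At stake is one specific protection. With normal ALP, a new combined rise ends treatment for good. With a stable, pre-existing raised ALP, the same rise is left to the isolated rows or to judgment, and the participant may be given capmatinib again. Section 4.5.1 lists liver test alterations among the findings seen with the drug, and adjuvant dosing runs for up to three years, so the rule is not idle.

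**Working it through.** The plan gives no figure of its own to reproduce here. All values below are multiples of ULN.

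**Inputs.** Entry ALP limit 5.0 (5.1). Combined stop: ALT or AST > 3 and TBL > 2, without cholestasis or hemolysis (Table 6-3). Cholestasis: ALP > 2.0 and R < 2.0 (footnote c). R = ALT / ALP (6.5.2.1). With metastatic disease excluded, the ALP-and-R form is the one that applies at entry.

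**Assumptions.** ALP stays at its entry value, R is calculated with ALP, TBL is > 2, and there is no hemolysis.

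**1. Before dosing.** With ALT at most 1, R is at most 1 / 2.1 = 0.48 at ALP 2.1 and 1 / 5 = 0.20 at ALP 5. Both are below 2.0, so footnote c is met.

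**2. Where the stop begins.** R < 2 means ALT < 2 x ALP.

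| Entry ALP | 2 x ALP | ALT range exempt from the combined stop |
|---|---|---|
| 2.0 or less | not applicable | none; stop applies above 3 |
| 2.1 | 4.2 | > 3 to < 4.2 |
| 3 | 6 | > 3 to < 6 |
| 4 | 8 | > 3 to < 8 |
| 5 | 10 | > 3 to < 10 |

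**3. A worked case.** ALP 4, ALT 6, TBL 2.5: R = 6 / 4 = 1.5, so the case is exempt. On the isolated rows, TBL is grade 2 and ALT is grade 3, and both interrupt dosing. For ALT, resolution to grade 1 or better within that row's first time limit means "7 days, then resume treatment at the same dose level"; the TBL row says the same in substance. So restart is at 400 mg b.i.d. if both resolve within 7 days, or at 300 mg b.i.d. if in 8 to 21 days. Beyond 21 days, Section 6.5.1 requires permanent discontinuation unless the sponsor approves an exception. If ALT is only > 3 to 5, the ALT row keeps the dose and bilirubin alone interrupts it.

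**4. AST.** R uses ALT only. With AST 15, ALT 1, TBL 2.5 and ALP 3, R = 1 / 3 = 0.33. The combined stop is not reached however high AST goes, as long as ALT stays low and ALP stays > 2. The isolated AST stop above 20 still applies.

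**5. Contrast with the other limb.** Take ALP 4 and normal baseline TBL. Entering with ALT 1.1 puts the participant in the elevated-baseline limb: the stop starts above 3 x 1.1 = 3.3, which is lower than 8.0. Entering with ALT 1.0 puts the participant in the first limb: the stop starts at 2 x 4 = 8.

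**6. GGT in place of ALP.** In the case in step 3, an assumed GGT of 1 gives R = 6 / 1 = 6, so the exception fails and the stop applies. With GGT above 3, R = 6 / GGT is again below 2 and the exemption returns.

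**The case against.** The strongest case against has five parts.

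- **Other safeguards are in place.** This stands. TBL > 2 x ULN interrupts dosing. Grade 3 TBL that takes longer to resolve leads to "7 days, permanently discontinue capmatinib" (the limit is 7 days), and grade 4 TBL or grade 4 ALT/AST also ends treatment. The 21-day limit remains. The work-up in 6.5.2.1 has no cholestasis exception, and confirmed cases without another cause are reported as SAEs. Section 9.1.1 requires stopping for a safety risk. A reader might infer that dosing simply continues or that the participant goes unmonitored; the Protocol does not support that.
- **GGT can replace ALP in R.** This stands in part. An isolated, long-standing raised ALP is a natural reason to suspect an extrahepatic source, and GGT is in the chemistry panel (Table 8-5). But the use is optional, is mentioned in 6.5.2.1 and not in footnote c, and does not help if GGT is also raised.
- **Footnote d asks for caution.** It does, but its own example of caution needs one parameter already at discontinuation, and it provides for restart. Read literally, it covers elevations below the thresholds, not elevations that pass them and are then excused. Use of the isolated rows is therefore the likely reading, not a stated one.
- **An ULN-based definition is a design choice, used consistently in two places.** True, but consistency does not make an unchanged pre-treatment value informative. The heading of the matching row in Table 6-4 suggests that the exception may have been meant for both limbs; that would widen the gap, not close it.
- **The population is hypothetical.** This stands, and it limits the weight of the point.

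**Conclusion.** The point holds as a cheap improvement for patient safety. As printed, a participant with normal baseline ALT, AST and TBL and entry ALP above 2 to 5 x ULN can satisfy the cholestasis definition before treatment. The mandatory combined stop is then deferred to ALT equal to twice the ALP multiple, and is not reached by AST alone. The loss is confined to that stop and shows itself as possible restart.

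The thresholds rest on stable ALP and on R calculated with ALP. If ALP falls to 2 x ULN or below, the exemption ends; if ALP rises, the ALT threshold rises with it. A reader might take the ranges as fixed for every such participant, but the GGT provision means they are not.

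Nor should a reader infer that anyone was exposed to this gap. SAP Section 4 records that recruitment ended at four participants, and no document shows that any of them had such an ALP or gives the share of eligible patients who would. Practical impact in this trial is low.

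**What to change.** In both footnote c of Table 6-3 and the definition in 6.5.2.1, replace the ALP condition (no bone metastasis) with: ALP above 2.0 x the higher of ULN and the participant's baseline ALP, together with R below 2.0. Baseline can follow the SAP's definition, the last value before first treatment. Changing only one of the two places would leave conflicting definitions. Inclusion criterion 6 and footnote d can stay as they are.

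**Check of the wording (multiples of ULN).**

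- At baseline ALP 2.1, 3, 4 and 5, the exception needs ALP above 4.2, 6, 8 and 10. A stable ALP never meets it, so the stop applies from ALT or AST > 3 with TBL > 2. This includes the AST-only case.
- There is no jump at baseline 2.0, where the limit is 4.0, next to 4.2 at baseline 2.1. Baseline 2.0 moving to 2.1 with ALT 4 (R = 4 / 2.1 = 1.90) is exempt today and would be stopped.
- A clear new rise is still exempt: ALP 4 to 9 with ALT 6 has 9 > 8 and R = 6 / 9 = 0.67.
- At baseline ALP of 1 or less nothing changes.

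**Cost.** A written amendment with IRB/IEC approval, touching two definitions. No new test is needed, because ALP is already in the chemistry panel at screening and at treatment visits. The clinical downside is that some participants with true cholestasis but a less than doubled ALP would be stopped permanently: ALP 4 to 6 with ALT 6 and TBL 2.5 is exempt today (R = 6 / 6 = 1.0) and would not be, since 6 is not above 8. The same holds for baselines between 1 and 2, where the limit rises from 2 to twice baseline.
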